# 6.4. Study Intervention Compliance

Participants will receive study intervention directly from the investigator and/or appropriate designee at the study site. The date and time of each dose administered will be recorded in the source documents and recorded in the case report form (eCRF). Deviations from the prescribed dosage regimen should be recorded in the eCRF.

# 6.5. Concomitant Therapy

Any medication or vaccine (including over-the-counter or prescription medicines, vitamins, and/or herbal supplements) that the participant is receiving at the time of enrollment or receives during the study must be recorded along with

- reason for use
- dates of administration including start and end dates, and
- dosage information, including dose for concomitant therapies of special interest.

Participants will be instructed to consult the investigator or other appropriate study site personnel before taking any new medications or supplements during the study.

The sponsor's medical monitor should be contacted if there are any questions.

## 6.5.1. Prior Medications

Participants must have been discontinued from following medications before enrolling in the study, as stated in Section 5.2:

- Biologic therapy (such as anti-IL-1, anti-IL-6 [tocilizumab or sarilumab], T-cell targeted therapies, interferon) must be discontinued 4 weeks or 5 half-lives, whichever is longer, prior to screening
- B-cell targeted therapies (rituximab): a washout period of 24 weeks or 5 half-lives (whichever is longer)
- TNF inhibitors: a washout period of 2 weeks or 5 half-lives (whichever is longer), and
- JAK inhibitor: a washout period of 1 week or 5 half-lives (whichever is longer).

In addition, strong inhibitors of OAT3 (such as probenecid) must be discontinued at study entry.

## 6.5.2. Required and Permitted Concomitant Therapy

Prophylaxis for VTE is required for all patients unless there is a major contraindication such as active bleeding events or history of heparin-induced thrombosis.

The following will be permitted as concomitant therapy during the study:

- Concomitant antibiotic, antiviral, antifungal, and/or antimalarial (background therapy in keeping with local clinical practice for management of COVID-19). Hydroxychloroquine and chloroquine are only permitted as concomitant medication if these are recommended or required by local COVID-19 treatment guidelines.
- Corticosteroid use should be limited unless indicated per standard of care for a concurrent condition such as, but not limited to, asthma, chronic obstructive pulmonary disease, adrenal insufficiency.

# 6.5.3. Prohibited Concomitant Therapy

The following will be prohibited as concomitant therapy during the study:

- Any biologic therapy (such as TNF inhibitors, anti- IL-1, anti-IL-6 [tocilizumab or sarilumab], T-cell or B-cell targeted therapies (rituximab), interferon, JAK inhibitors (other than baricitinib as study treatment), or immunoglobulin (IgG) for any indication.
- Live vaccines, including herpes zoster vaccination. Nonlive seasonal vaccinations and/or emergency vaccination, such as rabies or tetanus vaccinations, are allowed.
- Strong inhibitors of OAT3 (such as probenecid) that cannot be discontinued at study entry.
- Extracorporeal blood purification device to remove pro-inflammatory cytokines from the blood such as a cytokine absorption or filtering device, for example, CytoSorb®.

# 6.6. Dose Modification

Patients with eGFR  $\geq$ 30 mL/min/1.73 m^2 to <60 mL/min/1.73 m^2 at screening who are randomized to the baricitinib 4-mg dose will receive a 2-mg QD dose, to avoid exposures that exceed those of the 4-mg QD dose in patients with eGFR  $\geq$ 60 mL/min/1.73 m^2. Patients will remain on this dose during the study if eGFR  $\geq$ 30 mL/min/1.73 m^2 to <60 mL/min/1.73 m^2 at screening.

If after randomization eGFR decreases to less than 60 mL/min/1.73 m^2 but equal to or more than 30 mL/min/1.73 m^2, patients will receive a 2-mg QD dose (one tablet) until eGFR returns to eGFR  $\geq$ 60 mL/min/1.73 m^2.

Baricitinib is not recommended for use in patients with estimated GFR of <30 mL/min/1.73 m^2.

## 6.7. Intervention after the End of the Study

Baricitinib will not be provided to participants following completion of the study.

## 7. Discontinuation of Study Intervention and Participant Discontinuation/Withdrawal

In rare instances, it may be necessary for a participant to permanently discontinue study drug.

These sections describe reasons for a participant's

- permanent or temporary discontinuation of study drug, or
- discontinuation (withdrawal) from the study.

Discontinuation of specific sites or of the trial as a whole are handled as part of regulatory, ethical, and trial oversight considerations in Appendix 10.1, Section 10.1.9.

Note: In this study, discharge from the hospital prior to Day 14 is not considered early discontinuation from the study drug or from the study.

## 7.1. Discontinuation of Study Intervention

Study drug may be permanently discontinued or temporarily withheld during the study.

#### 7.1.1. Criteria for Permanent Discontinuation of Study Drug

Data collection and safety follow-up when study drug is permanently discontinued

If a patient permanently discontinues study drug early (that is, prior to hospital discharge or Day 14, whichever comes first), the patient should remain in the study and have the scheduled study assessments specified in the SoA (Section 1.3). Every effort should be made to encourage participants to remain in the study for the duration of their planned outcome assessments. Participants should be educated on the continued scientific importance of their data, even if they discontinue study drug.

Unless the participant withdraws consent or meets other criteria listed in Section 7.2, those who discontinue study drug early will remain in the study. The reason for participant discontinuation of study drug should be documented in the CRF.

If a patient who is not receiving study drug is unwilling or unable to continue the scheduled study assessments, the site personnel should attempt to collect as much follow-up information as possible, including, at minimum, information specified for an early termination visit (ETV) **and** information for the follow-up visits, including the Study Day 60 visit.

Criteria for permanent discontinuation of study drug

Possible reasons leading to permanent discontinuation of study drug include, but are not limited to, the following:

## **Participant decision**

• The participant requests to discontinue the study drug.

#### Prohibited concomitant medication use

• The participant requires treatment with a prohibited medication (Section 6.5.3).

#### Pregnancy

• The participant becomes pregnant during the study.

#### **Safety considerations**

- The participant should be discontinued if the participant develops any of the following conditions during the study:
  - new malignancy
  - human immunodeficiency virus (HIV)/acquired immune deficiency syndrome (AIDS) infection
  - active TB infection or evidence of latent TB (positive QuantiFERON-TB Gold assay or T-SPOT.TB or greater than 1 "indeterminate" result for QuantiFERON-TB Gold assay or a "borderline" result T-SPOT.TB assay)
  - active hepatitis B (HBV DNA) or hepatitis C (HCV RNA)
  - VTE (DVT/PE)
- The investigator, after consultation with the sponsor's designated medical monitor, determines that a systemic hypersensitivity reaction has occurred and is related to study drug administration.
- The participant experiences any 1 of the following events on 2 consecutive samples taken at least 48 hours, but no more than 1 week, apart.
  - Total white blood cells (WBC) <1000 cells/µL
  - Absolute neutrophil count (ANC) <500 cells/µL
  - Absolute lymphocyte count (ALC)  $\leq 200$  cells/ $\mu$ L
- The participant has an adverse event or serious adverse event or a clinically significant change in a laboratory value that, in the opinion of the investigator or sponsor, would preclude the participant from continuing to receive study drug.

#### Hepatic event or liver test abnormality

- Discontinuation of study drug because of abnormal liver tests should be considered by the investigator when a participant meets one of the following conditions after consultation with the medical monitor (see Section 8.2.6)
  - ALT or AST >8 times ULN or
  - ALT or AST >3 times ULN and (total bilirubin >2 times ULN or PT-INR >1.5)

#### Other reasons

• Unblinding: If an investigator, site personnel performing assessments, or participant is unblinded, the participant must be discontinued from the study drug and continue to post-treatment follow-up. In cases where there are ethical reasons to have the participant continue on study drug, the investigator must obtain specific approval from the sponsor or designee for the participant to continue.

#### 7.1.2. Criteria for Temporary Interruption (Withholding) of Study Drug

Study drug should be interrupted for:

- Absolute neutrophil count (ANC) <500 cells/µL

- Absolute lymphocyte count (ALC) <200 cells/µL

- ALT or AST >5 times ULN
- estimated GFR of <30 mL/min/1.73 m^2

Study drug may be restarted when these criteria are no longer applicable, at the discretion of the investigator. Retest timing and frequency is at the investigator's discretion.

Baricitinib is not recommended for use in patients with estimated GFR of <30 mL/min/1.73 m^2.

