### **Diagnostic assessments**

- [17] Have neutropenia (absolute neutrophil count <1000 cells/ $\mu$ L) (<1.00 x 10^3/ $\mu$ L or <1.00 GI/L)
- [18] Have lymphopenia (absolute lymphocyte count <200 cells/µL) (<0.20 x 10^3/µL or <0.20 GI/L)
- [19] Have alanine aminotransferase (ALT) or aspartate aminotransferase (AST) >5 times ULN
- [20] eGFR (Modification of Diet in Renal Disease [MDRD]) <30 mL/min/1.73 m^2.

Note: For each aforementioned diagnostic assessment (criteria 17, 18, 19, 20), 1 repeat testing is allowed during the screening period, and values resulting from repeat testing may be accepted for a participant's enrollment eligibility if the other eligibility criteria are met. In addition, these tests performed in the 24 hours prior to study entry will be accepted for determination of eligibility.

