## Safety monitoring

The principle investigator will monitor safety and laboratory data throughout the study and should discuss immediate safety concerns with the sponsor immediately upon occurrence or awareness to determine whether the participant should continue or discontinue the study intervention.

The sponsor will monitor the safety data, including adverse events and serious adverse events (SAEs), discontinuations, medical history, concomitant medications, vital signs, and clinical laboratory results by means of periodic blinded reviews and other appropriate methods. These methods include reviews by a functionally independent safety physician and/or clinical research scientist who regularly reviews SAE reports in real time and across studies, and who reviews applicable clinical safety and epidemiological publications from the literature. If this safety monitoring uncovers an issue that needs to be addressed by unblinding at the individual or group level, additional analyses of the safety data can be performed (Section 9.5 and Section 9.6).

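### White-cell count below 1000 is a permanent-stop criterion with no matching temporary hold, and the lymphocyte limits differ at exactly 200

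*Protocol*

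**What the plan says.** Three places in the protocol set haematology limits that bear on dosing.

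- **Permanent stop (7.1.1, Safety considerations).** The rule needs confirmation: "The participant experiences any 1 of the following events on 2 consecutive samples taken at least 48 hours, but no more than 1 week, apart". The events are "Total white blood cells (WBC) <1000" cells/µL, ANC <500 and ALC ≤200, the last with the boundary value included.
- **Temporary hold (7.1.2).** The list has four entries: ANC <500, "Absolute lymphocyte count (ALC) <200" cells/µL, ALT or AST above 5 times the upper limit of normal, and eGFR below 30. No confirming sample is required. There is no WBC entry. On resuming drug the section says: "Study drug may be restarted when these criteria are no longer applicable, at the discretion of the investigator".
- **Entry (5.2, Diagnostic assessments).** Criterion 17 excludes ANC <1000. Criterion 18 reads "Have lymphopenia (absolute lymphocyte count <200" cells/µL, so a patient at exactly 200 is eligible.

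The Schedule of Activities (1.3) places haematology on Days 1, 4, 7, 10, 14 and 28. Dosing runs to Day 14 or discharge, whichever comes first.

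**The concern.** A hold that acts on one sample protects the participant while a low count waits for confirmation. For ANC the protocol provides this: the limit that counts toward permanent stop also suspends drug at once. For WBC it does not. A first WBC below 1000 starts the two-sample rule, but no listed criterion suspends dosing in the meantime.

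For ALC the mismatch is one value. A participant can enter the trial at 200, remain at 200 without any worsening, never meet the hold criterion, and still satisfy the permanent-stop criterion.

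At stake are a few days of exposure to a JAK inhibitor at a count that the protocol itself treats as grounds for stopping, and consistent reading of the rules across sites. Protocol 2.3 names changes in lymphocytes and neutrophils among the labelled precautions, so clear limits are worth having. Nothing in the efficacy analysis is at stake: SAP 6.1 analyses the ITT population, and SAP 6.4.3 follows a treatment-policy strategy.

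**Working it through.** No sample-size, power or alpha figure is involved. The check compares the limits and then works out which counts fall between them.

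**Limits side by side (cells/µL)**

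| Count | Permanent stop, 7.1.1 (two samples) | Hold, 7.1.2 | Entry exclusion, 5.2 |
|---|---|---|---|
| WBC | <1000 | none | none |
| ANC | <500 | <500 | <1000 |
| ALC | ≤200 | <200 | <200 |

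**Size of the WBC gap.** Write WBC = ANC + ALC + other, with other ≥ 0. A sample counts toward stop through WBC but is not held when WBC <1000, ANC ≥500 and ALC ≥200.

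- Lowest WBC in the gap: 500 + 200 + 0 = 700. Below 700, at least one hold criterion must apply.
- Highest ANC: below 1000 − 200 = 800.
- Highest ALC: below 1000 − 500 = 500.

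The gap is therefore WBC 700 to <1000 with ANC 500 to <800 and ALC 200 to <500. Example: 550 + 250 + 100 = 900.

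**When it can arise.** ANC cannot exceed WBC, so criterion 17 rules out WBC <1000 at entry. The low count must develop on treatment, which makes Day 4 the first scheduled sample that can show it.

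**How long dosing can continue.** The scheduled pairs from Day 4 onward are Days 4–7, 7–10 and 10–14, with nominal gaps of 3, 3 and 4 days. All lie inside the 48-hour to 1-week window. A participant with the example counts on Days 4 and 7 is dosed for about 3 more days after the first sample, then meets 7.1.1, with no listed hold at any point. The laboratory tolerance of ±1 day per visit, or an unscheduled test, would change the interval.

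**ALC.** The stop and hold limits differ only at ALC = 200. Two samples at 200, on Days 4 and 7 for instance, count toward stop; neither triggers a hold.

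**What each change closes**

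| Change | Samples that count toward stop but are still not held |
|---|---|
| WBC <1000 added to hold list only | ALC = 200 with WBC ≥1000 |
| One ALC inequality only | WBC <1000 with ANC ≥500 and ALC above the hold limit |
| Both | none; the stop and hold conditions become identical |

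The last row follows by construction. It shows that the fix is complete, not that the gap is large.

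**The case against.** The strongest reply is that nothing in the protocol says the hold list must contain everything on the stop list. The hepatic rules do not match either: the hold is at ALT or AST above 5 times the upper limit of normal, while permanent stop is considered above 8 times, or above 3 times with raised bilirubin or PT-INR. The second of those has no hold counterpart. This has some force, but the hepatic text only asks the investigator to consider stopping, after consulting the medical monitor. It does not explain why ANC has a matching hold and WBC has none.

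The second reply is that the investigator can already act. The 7.1.1 reasons are open-ended ("Possible reasons leading to permanent discontinuation of study drug include, but are not limited to, the following"), and a clinically significant laboratory change can end treatment. Section 7.1 allows withholding in general. Under Safety monitoring in 8.2, immediate concerns go to the sponsor "to determine whether the participant should continue or discontinue the study intervention". Section 8.2.5 allows extra tests and requires clinically significant abnormal results to be repeated. All of this stands and keeps the point small. None of it supplies a WBC threshold for a hold.

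The third reply is that the gap is narrow: three counts must fall in limited ranges together, during at most 14 days of in-hospital dosing, and the ALC part is one value. That also stands.

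A reader might go further and infer that the restart sentence conflicts with the permanent stop. After ALC 150 (held) and then ALC 200 at 72 hours, the same sample would both lift the hold and complete the stop rule. The documents do not support reading this as a conflict. The 7.1.1 criteria are headed as permanent and apply in their own right, while restart under 7.1.2 is only permitted, at the investigator's discretion. The permanent stop prevails, and no added restart wording is needed.

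**Conclusion.** The point holds in limited form. The two sections agree for ANC. They disagree for WBC, which has a stop limit of 1000 and no hold, and for ALC at exactly 200. The practical consequence is that a participant with WBC 700 to <1000, ANC ≥500 and ALC ≥200 can receive about 3 to 4 further days of drug between scheduled samples and then meet permanent stop without any listed hold.

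This rests on two assumptions: that sampling follows the nominal schedule with no unscheduled test, and that the investigator does not use discretion to hold sooner. The ALC part also depends on the ≤ sign in 7.1.1, which should be checked against the source PDF. If the source reads <200, that part falls and the WBC part is unaffected.

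Few participants are likely to be affected, but the documents give no frequency and none is estimated here. It would be wrong to infer that participants are left unprotected or that the haematology rules disagree throughout. No efficacy analysis, sample size or error rate changes. This is a cheap improvement of low priority.

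**What to change.** 1. Add WBC <1000 cells/µL to the hold list in Protocol 7.1.2.
2. Use one ALC inequality in 7.1.1, 7.1.2 and exclusion criterion 18. The simplest edit is <200 in 7.1.1, which already matches the other two places; it takes the single value 200 out of the permanent stop. The clinical team may prefer ≤200 in 7.1.2 and criterion 18, which leaves the stop rule as it is but makes a patient at exactly 200 ineligible. The choice of threshold is theirs.

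The change is a few words and needs no new tests, because haematology is already scheduled. The costs are a few more temporary holds and a protocol amendment, which under 10.1.1 needs IRB/IEC approval before implementation. SAP 5.2 describes amendment E as the final one, so a further amendment to carry this change cannot be assumed. If dosing has ended, the correction is useful only for later protocols that reuse these rules.

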# 7.2. Participant Discontinuation/Withdrawal from the Study

Participant discontinuation (withdrawal from the study) is expected to be uncommon.

A participant may withdraw from the study in the following circumstances:

- at any time at his or her own request, or at the request of his or her designee (for example, parents or legal guardian)
- at the discretion of the investigator for safety, behavioral, compliance, or administrative reasons
- if the participant enrolls in any other clinical study involving an investigational medicinal product or enrollment in any other type of medical research judged not to be scientifically or medically compatible with this study
- if the participant, for any reason, needs to be transferred to another hospital or another hospital unit
- if the participant, for any reason, requires treatment with another therapeutic agent that has been demonstrated to be effective for treatment of the study indication. In this case, discontinuation from the study occurs prior to introduction of the new agent.

## Data collection and follow-up for participants who discontinue the study

At the time of discontinuing from the study, an ETV and final follow-up visits should be conducted, if possible, as shown in the SoA. See the SoA for data to be collected at the time of study discontinuation and follow-up and for any further evaluations that need to be completed. The participant will be permanently discontinued both from the study intervention and from the study.

## Withdrawal of consent for disclosure

If the participant withdraws consent for disclosure of future information, the sponsor may retain and continue to use any data collected before such a withdrawal of consent. If a participant withdraws from the study, he or she may request destruction of any samples taken and not tested, and the investigator must document this in the site study records.

## 7.2.1. Discontinuation of Inadvertently Enrolled Participants

If the sponsor or investigator identifies a participant who did not meet enrollment criteria and was inadvertently enrolled, then the participant should be discontinued from study treatment unless there are extenuating circumstances that make it medically necessary for the participant to continue on study treatment. If the investigator and the sponsor's clinical research physician agree that it is medically appropriate to continue, the investigator must obtain documented approval from the sponsor to allow the inadvertently enrolled participant to continue in the study with or without treatment with investigational medicinal product. Safety follow-up is as outlined in the SoA (Section 1.3), Section 8.2 ("Safety Assessments"), and Section 8.3 ("Adverse Events and Serious Adverse Events").

## 7.3. Lost to Follow-up

A participant will be considered lost to follow-up if he or she repeatedly fails to return for scheduled visits and is unable to be contacted by the study site. Site personnel are expected to make diligent attempts to contact participants who fail to return for a scheduled visit or were otherwise unable to be followed up by the site.

# 8. Study Assessments and Procedures

Study procedures and their timing are summarized in the SoA (Section 1.3). Protocol waivers or exemptions are not allowed. Adherence to the study design requirements, including those specified in the SoA, is essential and required for study conduct.

## 8.1. Efficacy Assessments

## 8.1.1. COVID-19 Clinical Status Assessment

The COVID-19 Clinical Status Assessment will be used to collect components needed to derive scores for the ordinal scales used in this study. This assessment will also collect the use of proning and reason for discontinuation of invasive mechanical ventilation.

The assessment will be completed on each day of the study by entering the assessment for the previous day (that is, midnight to midnight; 00:00 - 23:59 [24 hour clock]).

On Day 1, the patient's status at randomization will be reported.

On Day 2 the status will be reported for the period from randomization to midnight on Day 1.

The patient's clinical status will be captured daily through Day 29.

The hospitalization portion of the patient's clinical status will be completed daily, regardless of patient's discharge status or patient contact.

The patient's clinical status reflecting data for Day 28 (midnight to midnight) will be recorded in the Day 29 eCRF.

A clinical status assessment will be conducted via telephone visit for Day 60.

